The proposed study will use parallel-groups, randomized, sham controlled, double-blinded design in which 36 participants with motor incomplete SCI (AIS B – D level) will randomly assigned to receive tDCS combined with repetitive arm training (RAT) or sham tDCS combined with R-A training. During the first 20-minute participants (n=24) in the experimental group will receive 20 minutes of anodal tDCS (2 mA) on motor cortex contralateral to their trained side followed by RAT for 60 minutes. Participants (n=12) in the control group will receive 20 minutes of sham tDCS followed by RAT for 60 minutes. In the sham stimulation 2 mA of anodal current will be delivered in a ramp up and down fashion for 30 seconds at the beginning and 30 seconds at the end of 20 minutes of stimulation. Treatment will be administered at an intensity of 5 sessions per week for 2 weeks.

The randomization schedule will be provided by project statistician ([name]).

Outcome measure:

Feasibility outcome measure: Adherence with therapy will be measured as;
(1) the number of treatment sessions attended by each participant,
(2) number of drop-outs in each group,
(3) participant's perceptions of the use of study implementation (using the tDCS and exercise equipment, numerical rating scale with 'not difficult at all' at 0, and 'very difficult' at 10)
(4) participant's perceptions of usefulness of the intervention (numerical rating scale with 'not at all useful' at 0 and 'very useful' at 10).

The telerehabilitation intervention will be considered as feasible if at least 80% adherence rate is achieved (completed number of sessions \geq 8 out of 10), if attrition rate is no higher than 10% in each study group, if at least 40 minutes of 60 minutes exercise session is completed and if no serious adverse events took place (other than expected side effects from tDCS).

Clinical outcome measure: Primary clinical outcome measure is GRASSP prehension performance (Kalsi-Ryan et al., 2012). Secondary clinical outcome measures are grip strength and Spinal Cord Injury Independence Measure (SCIM III) (Itzkovich, Gelernter et al. 2007). Assessments will be repeated immediately after completion of 10 sessions and at 4-weeks follow-up.

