- (3) any joint contracture or severe spasticity in the affected upper extremity, as measured by a Modified Ashworth Score \geq than 3 out of 4.

6. Study Procedures:

Baseline Assessment (Duration: two to three hours): For both SCI subjects and healthy volunteers, the baseline assessment can be on the same visit as screening and will be performed in the Motor Recovery Laboratory by an evaluator blinded to subject's group assignment. Subjects (SCI) will be evaluated for upper extremity motor functions. Arm and hand functions will be assessed with Graded Redefined Assessment of Strength, Sensibility and Prehension (GRASSP), ASIA upper extremity scale (motor and sensory), grasp and release test and independence in daily functions will be assessed with SCIM-II.

Caregiver training: On the day of in-clinic baseline assessment, caregiver/family member who will be delivering the therapy at home will be trained on intervention protocol (localization of primary motor cortex to deliver the tDCS, operating the tDCS machine, operating the laptop and videoconference system, using special exercise equipment). Then they will take the tDCS device, exercise equipment and lap top computer home.

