Treatment at home (Duration: two hours): Home-treatment sessions will start on the following week (Monday through Friday) and continue for two-weeks (total 10 treatment sessions). During each treatment session primary motor cortex (C3 or C4 according to international EEG system) will be stimulated with anodal tDCS at 2mA for 20 minutes. Electrode sizes are 5x7cm, saline-soaked. Active (anodal) electrode will be placed over the primary motor cortex and reference electrode will be placed over contralateral supraorbital area. This single-position headgear include clearly labeled sponge markers to eliminate room for user error (see attached brochure for tDCS with head gear and sponge electrodes). Participants in the sham stimulation (control) group will use same stimulation location, however the duration of stimulation will be set to 30 seconds at the beginning and end of 20 minutes. This is a reliable method of sham stimulation as sensations arising from tDCS treatment occur only at the beginning of application (Gandiga, Hummel et al. 2006). Subjects often feel during current ramp up; however the same procedure will be adopted for sham stimulation (that will receive active current for 30 seconds only (insufficient time to produce meaningful changes) and therefore mimic the initial sensation associated with active stimulation. It should be noted that less than 3 minutes of tDCS induces no effects on cortical excitability (Nitsche and Paulus 2000) and also using 30 seconds of sham is a reliable method of blinding as shown by a randomized controlled study (Gandiga, Hummel et al. 2006).

Immediately after stimulation ceases, participants will continue with unilateral repetitive arm and finger exercises for 60 minutes. Exercise difficulty will gradually increase and adjusted as needed per participants tolerance. All treatment sessions will be supervised in real-time via videoconferencing by [name] in her office at the NeuroRecovery Research Center at TIRR/Memorial Hermann.

The tDCS device in this study (Soterix 1x1 tdCS mini-CT stimulator, see attachment), is specifically designed and developed for home-use. The intensity and duration of stimulation will be pre-programmed by [name]. After pre-programming device, it won't allow patient/caregiver to make changes. All session will be monitored remotely by [name]. After home-therapy ends, study participant will bring the FitMi and Music Glove devices, and the laptop back to the research lab.

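### The plan specifies neither stratification nor adjustment for AIS grade, so a 24:12 split of 36 people spanning AIS B to D can be unbalanced on severity by chance, at a cost in precision

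*Combined protocol and SAP*

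**What the plan says.** Section 4 (Study Design) states that "36 participants with motor incomplete SCI (AIS B – D level) will randomly assigned" to active or sham stimulation, each combined with arm training. The arm sizes are fixed: "participants (n=24) in the experimental group will receive 20 minutes of anodal tDCS" and "Participants (n=12) in the control group will receive 20 minutes of sham tDCS". On the method of allocation it says only that "The randomization schedule will be provided by project statistician". No sequence type, blocking, stratification factor, holder of the list or time of assignment is given.

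The schedule of activities in Section 6 lists the ASIA Impairment Scale and GRASSP at baseline and has no randomisation row. Section 6 also says that "the baseline assessment can be on the same visit as screening" and that the baseline evaluator is blinded to group. Caregiver training takes place on the day of the baseline assessment: "Then they will take the tDCS device, exercise equipment and lap top computer home". On the device it says "The intensity and duration of stimulation will be pre-programmed by" a member of the study team, after which patient and caregiver cannot alter the settings.

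Section 9 (Data analysis) compares GRASSP change between arms with a simple test that has no covariates. The mixed model has treatment arm and time as fixed effects and patient as a random effect. AIS grade enters neither analysis.

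**The concern.** Active versus sham is the only randomised comparison in the trial, and the smaller arm has 12 people. Enrolment covers three AIS grades. If people with different grades respond differently to two weeks of training, a sham arm that happens to hold too many or too few AIS D participants shifts the estimated stimulation effect in that particular trial. Analysing change from baseline removes differences in starting GRASSP level, but it does not remove differences in response by grade. With AIS grade absent from the analysis as well as the allocation, nothing written in the plan would limit such a shift or account for it. The information needed is already collected at the baseline visit.

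**Working it through.** **Inputs.** From Section 4: 36 participants, 24 active, 12 sham (24 + 12 = 36, ratio 2:1), AIS B to D. The AIS mix is not in the documents. I assume K of the 36 are AIS D, with K = 12, 18 or 24 (one third, one half, two thirds). Section 4 gives the sample size without a derivation, so there is no planned figure to reproduce beyond this sum.

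**Gap between arms.** Let x be the number of AIS D participants in the sham arm. The difference in AIS D share, sham minus active, is

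d = x/12 − (K − x)/24 = (3x − K)/24.

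Each person moved changes d by 3/24 = 12.5 points. For these K, the possible gaps are therefore 0, 12.5, 25, 37.5 points and so on.

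**Unstratified allocation.** With the totals fixed at 24 and 12, x is hypergeometric (12 drawn from 36, K of them AIS D). Its variance is 12 × (K/36) × (1 − K/36) × 24/35, and SD(d) = SD(x)/8.

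- K = 18: the variance is 12 × 0.5 × 0.5 × 24/35 = 2.057, so SD(d) = 1.434/8 = 17.9 points. A gap of 25 points or more means x ≤ 4 or x ≥ 8: 2 × (0.1070 + 0.0317 + 0.0053 + 0.0005) = 0.289. A gap of 37.5 points or more means x ≤ 3 or x ≥ 9: 2 × (0.0317 + 0.0053 + 0.0005) = 0.075.
- K = 12 (K = 24 is its mirror image): the variance is 12 × (1/3) × (2/3) × 24/35 = 1.829, so SD(d) = 1.352/8 = 16.9 points. A gap of 25 points or more means x ≤ 2 or x ≥ 6: 0.260. A gap of 37.5 points or more means x ≤ 1 or x ≥ 7: 0.058.

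| AIS D among 36 (assumed) | SD of gap | P(gap ≥ 25 points) | P(gap ≥ 37.5 points) |
|---|---|---|---|
| 12 or 24 | 16.9 points | 26.0% | 5.8% |
| 18 | 17.9 points | 28.9% | 7.5% |

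With more extreme mixes the risk is smaller: 21.9% and 3.6% for K = 9, and 14.9% and 1.0% for K = 6.

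**What a gap does to the estimate.** Let δ be the difference in mean GRASSP change between AIS D and AIS B/C, taken as the same in both arms. A gap of 25 points then shifts the unadjusted active versus sham difference by 0.25δ, and a gap of 37.5 points by 0.375δ. The direction is as likely to favour one arm as the other, and the average shift over allocations is zero. The documents give no value for δ.

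**Role of the 2:1 ratio.** For K = 18, a 1:1 split of 36 gives SD(d) = 16.9 points against 17.9. The risk comes mainly from the small total without stratification.

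**The proposed scheme.** I simulated 2:1 allocation in randomly chosen blocks of 3 and 6 within two strata (D; B/C), for AIS D counts from 11 to 24, with 20,000 runs each. The largest gap seen was 16.7 points, and no run reached 20 points. The sham arm ended between 10 and 14, and was exactly 12 in about 51% to 77% of runs depending on the mix.

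**The case against.** **The plan is silent; it does not rule stratification out.** The statistician's schedule may already be stratified. That stands: the finding is that stratification is not specified. If it exists, the remedy is to write it down. The missing adjustment is different, because Section 9 lists the fixed effects and AIS grade is not among them.

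**The headline percentage depends on the threshold.** Because the gap moves in 12.5-point steps, any threshold just above 25 points cuts the probability from 26–29% to 6–7.5%. That stands, and both figures are given.

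**Chance imbalance under valid randomisation is not bias.** This also stands. A reader might infer that severity imbalance would confound the comparison. The documents do not support that: the shift averages zero over allocations, and what is lost is precision. No link between AIS grade and GRASSP change is shown, every participant must be able to grip a small object, and change scores largely deal with differences in starting level. Only differential response by grade remains.

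**Early knowledge of assignments is not shown.** A reader might infer from the supplied schedule, the same-day device handover and the possible same-day screening that the team holds the list and knows the next assignment while judging eligibility. The text does not say the team holds the list. The order in Section 6 (baseline assessment, caregiver training, then the device goes home) leaves room for assignment after eligibility and baseline GRASSP, and the baseline evaluator is blinded. What remains is missing detail on when assignment happens and who holds the list.

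**Conclusion.** The point holds as one about precision and specification. Section 4 specifies no stratification and Section 9 no adjustment for AIS grade, although the grade is collected at baseline. If one third to two thirds of participants are AIS D and allocation is unstratified with fixed totals, a gap of 25 points or more arises in 26% to 29% of allocations, and one of 37.5 points or more in 6% to 7.5%. How much precision is lost depends on how strongly AIS grade predicts GRASSP change, which the documents do not quantify. The feasibility aim, which is descriptive, is hardly affected. The unstated time of assignment and holder of the list are a secondary clarification and not evidence that concealment fails. The change is worth making because it is cheap and uses data already collected.

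**What to change.** **Section 4.** State that participants are randomised 2:1 to active or sham, stratified by AIS D versus B/C, in randomly varying blocks of 3 and 6.

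**Section 9.** Include the AIS stratum as a covariate in the active versus sham comparison of GRASSP change (a linear model with arm and stratum) and as a fixed effect in the mixed model.

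**Secondary clarification, Sections 4 and 6.** State that the statistician holds the list and releases each assignment only after eligibility and baseline GRASSP are recorded and before the device is programmed. Add a randomisation row to the schedule of activities at that point.

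**Cost.** The text changes are a few sentences, one schedule row and one model term, with no new data collected. The stratum uses one degree of freedom. Unfinished blocks may leave the sham arm at 10 to 14 instead of exactly 12, so the arm sizes in Section 4 should be described as targets. The schedule for participants not yet enrolled would need to be regenerated, and there may be a short wait at the baseline visit while the assignment is released.

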There is evidence that treatment intensity has a profound effect on motor recovery. High-dosage, high-intensity repetitive training of arm movements or functional tasks can provide better functional outcome (Whiteneck, Gassaway et al. 2011, Backus, Gassaway et al. 2013, Jones, Evans et al. 2014, Brazg, Fahey et al. 2017, Francisco, [name] et al. 2017, Wouda, Lundgaard et al. 2018) However, many patients do not receive high doses of rehabilitation therapy for reasons that include cost, difficulty traveling to the location where the therapy is provided, shortage of regional rehabilitation care, and poor adherence with assignments. Furthermore, even when patients can access in-clinic rehabilitation therapy, the amount of therapy provided is limited, averaging 32 arm movements per session (Lang, Macdonald et al. 2009). In this regard, through telerehabilitation systems clinicians have the possibility of delivering long rehabilitation trainings at patient's homes.

In summary current options for treatment of upper extremity functions in persons with tetraplegia have been limited to in-clinic therapy programs. We suggest that alternative delivery of rehabilitation services should be investigated to provide therapy. Therefore, in the proposed study we aim to investigate the feasibility and clinical effectiveness of remotely-supervised home-based telerehabilitation protocol aiming to improve arm and hand functions in adults with tetraplegia.

3. Objectives:

Specific Aim 1: to determine feasibility and adherence of remotely-supervised home-based upper-limb telerehabilitation program

Specific Aim 2: to determine functional activity level in changes of measurements of upper-limb motor function, grip strength and health-related quality of life.

4. Study Design:

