Brain motor cortex function: Functional near-infrared spectroscopy (fNIRS) device will be used to measure and record relative changes in oxygenated and deoxygenated hemoglobin from the motor cortex of the brain. This in turn will help examine and understand the effects of a combined tDCS/robotic assisted arm training treatment upon motor-related brain activity. FNIRS emits near-infrared light (740nm/850nm) into the head and acquires the amount of light returning using a detector positioned 3cm from the light source. It is a portable, non-invasive device similar to EEG and has been used in multiple research studies investigating brain function under various task-oriented settings. One major risk the fNIRS device poses is potential eye damage if the infrared light-emitting diodes (IR LEDs) are shined into an individual's eyes for an extended amount of time. This will be mitigated however by ensuring that the investigator leaves the device powered off before placing it on the user's head. An additional minor risk includes a mild discomfort caused by the tightness of the headband and straps. The investigator will adjust the device to provide optimal comfort to the subject. fNIRS will be performed at the baseline, immediately after completion of 10 sessions treatment and at 4-week follow-up.

5. Study Population:

36 adults with chronic incomplete cervical SCI will be recruited from TIRR/Memorial Hermann, local healthcare providers and from support groups in Houston area.

Participants will be included if they have:

- (1) diagnosis of a chronic incomplete cervical lesion as defined by the American Spinal Injury Association Impairment scale classification and at least for 6 months post injury;
- (2) upper-extremity weakness associated with tetraplegia with minimal residual thumb and index finger movement sufficient to grip small objects such as marble;
- (3) age 18 - 70 years;
- (4) no brain injury;
- (5) no planned alteration in upper-extremity therapy or medication for muscle tone during the course of the study;
- (6) no contradiction to tDCS
- (7) access to internet at home.

Subjects will be excluded if they have:

- (1) prior history of seizure;
- (2) modifications in chronic use of neuroactive medication (e.g., neurostimulants, anticonvulsants, or antidepressants) during study period (between baseline and follow-up);

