Schedule of activities

Event	Baseline (Day -6 to 0)	Treatment Sessions (1-10)	Post-treatment (Day 5±3)	Follow-up 1 (Day 35±5)
Informed Consent	X			
Inclusion/Exclusion Criteria	X			
Demographics	X			
Medical and Social History	X			
Medication Checklist	X		X	X
ASIA-Impairment Scale	X		X	X
GRASSP	X		X	X
Grip Strength				
NHPT	X		X	X
SCIM-II	X		X	X
tDCS	X			
Music Glove and FitMi arm training		1-10		
tDCS-Side Effects Questionnaire		1-10		
Pain and Fatigue		1-10		
Participant-tDCS &Arm Exercise Survey		1,6,10		
Participant- Usefulness of Intervention Survey			X	X
Caregiver tDCS&Arm Exercise Survey		1,6,10		
Caregiver-Usefulness of Intervention Survey			X	X

Post-treatment and Follow-Up Assessment (Duration: two-hours): During this period subjects will be asked to come within a-week after they have completed the study and at week 4 for follow-up. GRASSP, Grip Strength, SCIM-II and fNIRS measurements will be repeated at post-treatment visit and at 4-week follow-up visit.

7. Potential Risks/Discomforts

tDCS: Transcranial direct current stimulation (tDCS) is a technique that poses a non-significant risk to subjects. The safety of this technique has been addressed and tested by multiple researchers (e.g., Hummel, et al., (Hummel and Cohen, 2005); Fregni, et. al., (Fregni et al., 2006a, Iyer et al., 2005); Nitsche, et al., (Nitsche et al., 2003c, Nitsche et al., 2003b, Nitsche et al., 2003a), (Nitsche et al., 2004); Priori, et al., (Priori, 2003)). Researchers have concluded that tDCS, as applied in a manner similar to our proposed protocol, induces only temporary mood, cognitive / motor effects, and no negative side effects. No undesirable or long-lasting effects have been reported, nor have any subjects reportedly abandoned a study due to discomfort. The most common side effects according to a recent consensus are: headache, dizziness, nausea, itchy sensation as well as irritation under the area of the electrodes (Nitsche et al., 2008). Researchers at the National Institute of Neurological Disorders and Stroke (NINDS), Iyer et al., (2005) (Iyer et al., 2005) conducted a safety study on tDCS, investigating 20-minute sessions of 1 mA and 2 mA current stimulation with healthy controls (n=103). No negative effects were identified. Nitsche and colleagues (2004) found no measurable structural changes in brain tissue due to tDCS (Nitsche et al., 2004). Finally, two recent studies showed that

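### As written, the feasibility rule counts every serious adverse event whatever its cause or timing, so one event unrelated to the home programme gives a verdict of not feasible

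*Combined protocol and SAP*

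**What the plan says.** Section 3 makes feasibility the first aim: "Specific Aim 1: to determine feasibility and adherence of remotely-supervised home-based upper-limb telerehabilitation program". Section 4, under the feasibility outcome measure, gives the only rule that turns the data into a feasible or not-feasible verdict. It joins four conditions, and all must be met:

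- at least 8 of 10 sessions completed;
- "if attrition rate is no higher than 10% in each study group";
- at least 40 of the 60 exercise minutes completed;
- "if no serious adverse events took place (other than expected side effects from tDCS".

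Other sections bear on the last condition but do not define it.

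- **Section 6, schedule of activities.** The "tDCS-Side Effects Questionnaire" and the pain and fatigue ratings are collected at sessions 1 to 10. There is no row for SAEs or for their relationship to treatment.
- **Section 7.** The expected tDCS effects are minor: headache, dizziness, nausea, itching, irritation under the electrodes, tingling and skin redness.
- **Section 8.** The only statement is that the study has no DSMB.
- **Section 9.** Feasibility and adherence are to be summarised descriptively.

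**The concern.** The condition sets a limit of zero SAEs and exempts one class of event by cause. The exempted class consists of effects of the stimulation, which are related events. Unrelated events are not exempted. A hospital admission that has nothing to do with the stimulator, the exercise equipment or the training would therefore make the programme not feasible by itself, even if every participant completed every session.

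The rule also gives no period. An event during the two weeks of home treatment and an event weeks later, before follow-up, count the same. At stake is the verdict on Specific Aim 1, which an event that says nothing about home delivery could reverse. If the study team then wished to set such an event aside, it would have to do so after knowing what had happened, which is what a prespecified criterion is meant to prevent.

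**Working it through.** The plan states no SAE rate and no figure for this condition, so there is nothing to reproduce. The check is first textual, then an illustration.

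**1. Does any text limit the condition by cause?** The sentence itself exempts only expected tDCS effects. Sections 6 to 9 contain no SAE definition, no causality assessment and no rule for attributing events. The answer is no.

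**2. Does any text limit it by time?** No. The candidate periods differ a good deal. Home treatment is described as "Home-treatment sessions will start on the following week (Monday through Friday) and continue for two-weeks (total 10 treatment sessions" in all, so Monday of week 1 to Friday of week 2 is 12 calendar days. Participants are then asked to "come within a-week after they have completed the study and at week 4 for follow-up", while the schedule puts follow-up at day 35±5. If follow-up is timed from the last session (an assumption), the first home session to follow-up spans 12 + 28 = 40 days, or 12 + 30 = 42 to 12 + 40 = 52 days. At a constant event rate, the longer period carries about 40/12 = 3.3 to 52/12 = 4.3 times the risk of the shorter one.

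**3. How easily could the condition fail?** The input from the plan is n = 36 (Section 4). The assumed input is p, the risk per participant of at least one unrelated SAE over the period counted, with participants independent. The chance of failing is 1 − (1 − p)^36.

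| Assumed p | Chance that the condition fails |
|---|---|
| 0.5% | 16.5% |
| 1% | 30.4% |
| 2% | 51.7% |

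Inverting the formula, the chance is 10% at p = 1 − 0.9^(1/36) = 0.29%, and 50% at p = 1 − 0.5^(1/36) = 1.9%.

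**4. How often would this condition alone decide the verdict?** Less often, because the rule may fail for other reasons. The 10% attrition limit allows at most 2 drop-outs of 24 (10% of 24 is 2.4) and 1 of 12 (10% of 12 is 1.2). For an assumed drop-out risk d, attrition is acceptable with probability P(Bin(24, d) ≤ 2) × P(Bin(12, d) ≤ 1). Multiplying by the 30.4% from step 3 (p = 1%):

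| Assumed d | Attrition condition met | SAE condition alone decides, at most |
|---|---|---|
| 2% | 0.988 × 0.977 = 0.965 | 0.304 × 0.965 = 29% |
| 5% | 0.884 × 0.882 = 0.779 | 0.304 × 0.779 = 24% |
| 10% | 0.564 × 0.659 = 0.372 | 0.304 × 0.372 = 11% |

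These are upper bounds. They take adherence and session length as always met, and SAEs as independent of drop-out.

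**The case against.** **The narrower reading is natural.** The sentence judges the telerehabilitation intervention, and its parenthesis speaks of side effects, so the authors may have meant only events caused by the programme. That is possible, but the text does not say it. If it was meant, one clause settles it.

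**A plain all-cause count is a defensible conservative choice.** The trial is small, caregivers deliver treatment at home, there is no DSMB, and a count leaves the team no room to explain events away. This stands in part: a relatedness judgement does add discretion. It does not rescue the rule, because an unrelated event is no evidence about the programme that the rule judges.

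**The magnitude rests on assumed rates.** This stands. The documents do not show whether 0.29%, 1% or 1.9% is realistic.

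Two stronger readings are tempting, and the documents do not support them.

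- A reader might infer a further gap because attrition is required within each group while the SAE condition names no arm. A percentage needs a denominator, but a zero count does not: zero overall is zero in each group. Both arms receive the home programme, so the count covers all 36.
- A reader might infer that the exemption could excuse a serious event caused by stimulation. It is confined to expected effects, and those listed in Section 7 are minor. A serious event outside that list counts as written.

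**Conclusion.** The point holds as one about definition. The rule has a zero limit and no restriction by cause or period, so applied as written a single unrelated SAE gives not feasible whatever the other three conditions show. This follows from the wording and needs no assumed rate.

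The importance is minor. The verdict leads to no progression or stopping decision, and a reader of the descriptive results would see the event beside the other criteria. The figure of about 30% holds only at an assumed 1% risk per participant, with independent participants and all 36 counted. It is the chance that this condition fails, which is not the same as the chance that it alone decides the verdict.

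**What to change.** Reword the condition in Section 4 along these lines: *no serious adverse event judged, before unblinding, to be at least possibly related to tDCS (active or sham), the home devices or the exercise programme, from the first home session to the follow-up visit.*

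Add an SAE row to the schedule, and list all SAEs by arm and relatedness whatever their cause. The listing should include any event linked to fNIRS, since Section 4 states that "One major risk the fNIRS device poses is potential eye damage". Such events should be reported but should not decide feasibility: fNIRS is an outcome measurement made at the assessment visits, not part of the home programme.

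The sponsor should name who judges relatedness, from staff blinded to arm. Section 6 says that the baseline assessment "will be performed in the Motor Recovery Laboratory by an evaluator blinded to" group assignment, but that role is described for the assessments. Nothing assigns it the causality judgement.

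The cost is one reworded condition, one schedule row and one judgement per SAE. No treatment, visit or sample size changes. The downside is some added discretion, which the full listing keeps visible.
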